Study Design. The study will be a person-randomized clinical trial comparing the effects of the eCPP tablet-based intervention to an enhanced usual care control condition (Table 1). Parents ($n = 312$) of 2- to 5-year-old children will be recruited from 4 primary care practices and randomly assigned to either the eCPP or control condition. Randomization will occur within sites at the participant level. Intervention parents ($n = 156$) will complete the 6 modules of the eCPP over a period of 3 months (~2 weeks/module; intervention phase) with ongoing access to the program (reference phase) throughout the remainder of the study period. Control condition parents ($n = 156$) will receive tablet-based parenting materials that they would normally receive at their primary care practice (e.g., information regarding nutrition, immunization, and exercise) and have access to the materials over the same intervention time period. Data collection in both conditions will occur at baseline and at 3, 6, and 12 months post-baseline. A descriptive design will be used to evaluate implementation of the eCPP from the perspective of practice sites, clinicians, and parents. Guided by the RE-AIM framework, we will use surveys, electronic health records, data usage metrics, and post-implementation assessments to evaluate the implementation process over the study period.

Measures.

Aim 1: Randomized Control Trial. All measures are written at the 5th grade reading level and administered on an Android tablet as computer assisted, self-interviews (CASIs). An audio option (audio-CASI) is available if parents prefer to listen to the questions. All control and outcome data are obtained by parent self-report and will be collected at each of the 4 data collection time points (baseline, 3, 6, and 12 months post baseline). Previous findings from RCTs of the group-based CPP have found significant findings across three sources of data: parent self-report, teacher report and parent-child observation.^{14,24} In these studies, the parent self-report findings have consistently agreed with other methods of measuring parent and child outcomes. For this reason, the source of parenting and child outcome data for this study will be parent self-report alone.

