All analyses for Aim 1 will be performed on an intent-to-treat basis. As multiple dependent variables are being examined, a repeated-measures multivariate analysis of variance (assessment x intervention condition) will be conducted to ensure control of experiment-wise Type-I error, and to perform an initial assessment of intervention effects. We will then test intervention efficacy using multilevel growth models⁹⁰⁻⁹² with three levels (assessments [Level 1] within parent [Level 2] within primary care practice site [Level 3]). Intervention condition will be dummy coded (eCPP vs. control) at Level 2, and covariates at site-level (e.g., clinic size) or parent-level (e.g., age, race/ethnicity) will be included at the appropriate level of analysis. By including baseline measures of the outcome variable being tested as a covariate at Level 2 (parent level) and setting the intercept at the 3-month assessment, we will be able to test Hypothesis 1A (intervention effects between baseline and 3-month assessment) as the main effect of intervention condition (i.e., controlling for baseline level of the outcome being tested). The condition x time interaction will then serve to test differential change in outcome measures following the 3 months of active intervention, and planned contrasts will be estimated to test Hypothesis 1B (maintenance of intervention effects at 6 and 12 months).

Aim 2. Compare the cost-effectiveness of the eCPP intervention relative to control for parenting and child outcomes. **HYPOTHESIS 2:** The eCPP is cost-effective relative to control for parenting and child outcomes.

We will assess cost-effectiveness of eCPP from the societal perspective, including costs borne by the program, health care system, and parent. We will conduct additional analyses from the program, health care system, and parent perspectives separately. For the cost measurement, quantities of resources used and their associated prices will be collected for the eCPP (either prices paid or value of the clinician time) and participant (i.e., value of participant's time to use the eCPP). Program and parent costs will be calculated for the 12-month study duration and summed to calculate total cost per parent. All costs will be valued in 2015 dollars.

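### The first Aim 1 test, a repeated-measures MANOVA, names no baseline covariate and, on its natural reading, has less power than a baseline-adjusted omnibus test of the same outcomes

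*Combined protocol and SAP*

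**What the plan says.** Under Study Design, "Parents ($n = 312$) of 2- to 5-year-old children will be recruited from 4 primary care practices", with 156 allocated to each condition. "Randomization will occur within sites at the participant level", and "Data collection in both conditions will occur at baseline and at 3, 6, and 12 months post-baseline".

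The Aim 1 part of the analytic plan has two steps. The first is an omnibus test: "a repeated-measures multivariate analysis of variance (assessment x intervention condition) will be conducted to ensure control of experiment-wise Type-I error". It is also meant to give a first look at intervention effects. Only two factors are named. There is no covariate and no site term, and neither the levels of the assessment factor nor the outcomes that enter are listed.

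The second step is a set of three-level growth models, one outcome at a time, with site as the top level and the intercept at 3 months. Here the plan does adjust for baseline, by "including baseline measures of the outcome variable being tested as a covariate at Level 2 (parent level". No rule says whether this step depends on a significant result in the first.

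**The concern.** The plan uses the baseline score as a covariate where it tests efficacy, but apparently not in the omnibus test that precedes it. If baseline is one of four repeated measurements, the interaction compares the arms on change from baseline, which fixes the slope on baseline at 1. In a randomized trial both change scores and baseline adjustment are unbiased. In large samples adjustment is never less efficient, and it is clearly more efficient unless the correlation between visits is high.

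At stake is power in the step that carries the experiment-wise error control. If that step is used as a gate, a real effect of the eCPP could be stopped there because a less efficient test was chosen. If it is not a gate, the only loss is a less sensitive first look at the effects.

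**Working it through.** **Inputs from the documents.** 156 + 156 = 312 parents, four practices, four assessments, five primary outcome domains. The scales in the Measures section can also be counted as 18 subscales: PQ 3, PARYC 3, PSOC 2, PSI-SF 3, ECBI 2, SDQ 5. There is no power calculation to reproduce: alpha, effect size, SD and correlations are not given.

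**Assumptions.** Two-sided 5%; complete data; the same correlation ρ between any two visits, for ρ from 0.5 to 0.8; correlation 0.4 between outcomes; the same standardized effect d on every outcome at 3, 6 and 12 months; no effect at baseline.

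**Variance of the follow-up mean, in units of the outcome variance.**
- Change from baseline: V = (1 + 2ρ)/3 + 1 − 2ρ. At ρ = 0.5 this is 0.667 + 1 − 1 = 0.667.
- Baseline as covariate: V = (1 + 2ρ)/3 − ρ². At ρ = 0.5 this is 0.667 − 0.25 = 0.417, which is 37.5% lower.

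**Omnibus power.** With two arms both tests are exact F tests on 3p contrasts for p outcomes, and the noncentrality is λ = (156/2) × m × d²/V. Here m = p/(1 + 0.4(p − 1)), which is 5/2.6 = 1.923 for five outcomes. Denominator degrees of freedom are 312 − 3p − 1 = 296 for the planned test and 312 − 4p − 1 = 291 for the adjusted test. For the adjusted test λ is multiplied by (312 − p − 3)/(312 − 2) = 304/310, to allow for chance baseline imbalance. At ρ = 0.5 and d = 0.25:
- planned: 78 × 1.923 × 0.0625/0.667 = 14.06
- adjusted: 78 × 1.923 × 0.0625/0.417 × 304/310 = 22.06

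Five outcomes, d = 0.25:

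| ρ | V, change | V, adjusted | λ, planned | λ, adjusted | Power, planned | Power, adjusted |
|---|---|---|---|---|---|---|
| 0.5 | 0.667 | 0.417 | 14.06 | 22.06 | 61.7% | 85.6% |
| 0.6 | 0.533 | 0.373 | 17.58 | 24.63 | 74.2% | 90.0% |
| 0.7 | 0.400 | 0.310 | 23.44 | 29.66 | 88.2% | 95.5% |
| 0.8 | 0.267 | 0.227 | 35.16 | 40.56 | 98.3% | 99.4% |

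Other settings at ρ = 0.5:
- five outcomes, d = 0.30: 81.6% against 96.8%
- 18 subscales, d = 0.30: 57.0% against 81.1%
- five outcomes, effect fading from 0.30 to 0.20 to 0.10: 65% against 81%

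**Check by simulation** (3,000 runs, five outcomes, ρ = 0.5). Rejection rates, planned against adjusted, were 4.7% and 4.9% with no effect, 62% and 86% at d = 0.25, and 82% and 97% at d = 0.30.

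**The condition main effect of the same MANOVA.** It averages four visits, one of them before treatment. Its power at ρ = 0.5 and d = 0.25 is 58%, so it does not make up the loss.

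**Site.** A constant site difference cancels from within-parent changes. In simulation (four sites of 78, ρ = 0.6, outcome correlation 0.3, d = 0.2), power without and with site was 64.0% and 64.1% at a site intraclass correlation of 0.05, and 63.1% and 63.2% at 0.10. Rejection with no effect was 5.4% to 5.6% throughout. When sites also varied by visit (variance share 0.02), the test without site was slightly conservative, at 3.8% against 4.7%, and its power was 58% against 62%.

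**The case against.** The best reply is that efficacy is tested in the growth models, which already adjust for baseline and carry site, so the first step is only preliminary. That stands as far as it goes: the plan states no gate, and without one nothing is blocked. Nor would a non-significant omnibus test contradict a significant single-outcome model, since the two test different hypotheses.

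A second reply is that the plan never says baseline is a level of the assessment factor. In the growth models the same word seems to cover follow-up visits only. This also stands, but it does not remove the point. If only 3, 6 and 12 months enter, an effect that is equal at all three gives no interaction at all, so that test has 5% power. The unadjusted condition main effect has 83% power at ρ = 0.5 and d = 0.25, against 97% with baseline as covariate. Adjustment helps on either reading.

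Four stronger readings are tempting and are not supported.
- A reader might infer that error control fails. It does not: the rejection rate with no effect stays near 5%, and only power is lost.
- A reader might blame the missing site term. The figures above show that it matters little.
- A reader might conclude that the MANOVA is weaker than the models that follow it. That is not general. For a one-outcome 3-month analysis of covariance at an unadjusted 5%, λ = 78 × d²/(1 − ρ²). At ρ = 0.6 and d = 0.30 this is 78 × 0.09/0.64 = 10.97, which gives 91% power, the same as the planned MANOVA. At ρ = 0.5 and d = 0.25 the MANOVA is behind (62% against 72%); at ρ = 0.8 and d = 0.25 it is ahead (98% against 96%).
- A reader might take the adjusted omnibus test to test the same effect as the growth models. It does not: Hypothesis 1A is examined outcome by outcome at 3 months.

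**Conclusion.** The point holds as an efficiency loss in the first Aim 1 step, judged against a baseline-adjusted omnibus test of the same outcomes. With five outcomes and d = 0.25 the loss is about 24 percentage points of power at ρ = 0.5, 16 at 0.6, 7 at 0.7 and 1 at 0.8. These sizes rest on assumed effects and correlations, on complete data, and on baseline being a level of the assessment factor, which is inferred from the four data collection points and is not stated. How much it matters depends on whether the MANOVA is to act as a gate, and the plan leaves that open. This is a worthwhile, inexpensive improvement. It is not a flaw that invalidates the Aim 1 tests.

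**What to change.** Replace the first-step MANOVA with a multivariate analysis of covariance. Use the 3-, 6- and 12-month scores as outcomes and the baseline scores of the same outcomes as covariates, and take the joint condition effect over the three follow-ups as the omnibus test. Site may be added as a factor (3 degrees of freedom for four practices), but the gain does not depend on it.

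This is a change of about one sentence and needs no new data, staff or parents. The price is one degree of freedom per baseline covariate, 5 to 18 out of about 310, which the power figures above already include. The same sentence should list the outcomes that enter. Whether a significant omnibus result is required before the growth models are read is a separate decision, which this change does not settle and which the plan should also state.

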Study Protocol and Statistical Analysis Plan

Identifiers: NCT02723916

Title: Parent Training in Pediatric Care: A Self Directed Tablet-Based Approach

Date of Document: September 1, 2015

The **specific aims** are:

Aim 1. Test the direct effects of the 6-module eCPP on parenting outcomes (parenting behavior, self-efficacy, and stress) and child outcomes (child problem and prosocial behavior) compared to an enhanced usual care control condition among low-income parents with young children seen in primary care.

HYPOTHESIS 1A: Relative to parents in the control condition, parents in the eCPP condition will report greater improvements in parenting and child outcomes at the 3-month assessment.

HYPOTHESIS 1B: The improvements in parenting outcomes and child outcomes the eCPP condition relative to the control condition will be maintained through the 6- and 12-month assessments.

Aim 2. Compare the cost-effectiveness of the eCPP relative to control for parenting and child outcomes.

HYPOTHESIS 2: The eCPP is cost-effective relative to control for parenting and child outcomes.

Aim 3. Quantify the levels of program implementation of the eCPP in primary care using the RE-AIM

framework. **RESEARCH QUESTION 3:** What is the degree of Reach, Efficacy, Adoption, Implementation, and Maintenance of the eCPP intervention in pediatric primary care

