IMPLEMENTATION: Assessment of the delivery of the introduction of the study by clinicians and associated costs.	Proportion of clinicians that introduce the study to parents of patients aged 2-5 at well-child visits (source: EHR). Tracking and monitoring any implementation adaptations by the clinicians (source: clinicians). NOTE: Evaluation of implementation-related cost will occur as part of data collection and analysis of Aim 2 [Specific Aim 2- cost-effectiveness analysis] .
MAINTENANCE: Evaluation of the practice site maintenance of implementation procedures and participant level maintenance of behavior change.	Evaluation of maintenance of procedures across the study period at the practice sites (source: recruitment rates, # of parents introduced to the study monthly). # of follow-up orientation sessions for clinicians. Assessment of implementation challenges and facilitators, and sustainability of activities in clinical practice (source: post-implementation interviews with clinicians). Maintenance of behavior change over time will be assessed as part of the RCT arm of the study. [Specific Aim 1- RCT (Hypothesis 1b)]

EHR = Electronic Health Record. ^aThe Technology Inventory includes 18 items for parents to respond to about their use and ownership of technology. ^bThe Primary Clinician Survey⁸⁶ is a 25-item measure developed by Metzler and colleagues for their 2014 NIH-funded grant “Parenting Help Online Study” to assess pediatric primary care clinicians’ current practices in helping parents with child behavior problems and parenting concerns. The measure will be used with permission by the authors; no reliability data has been reported. (Appendix B)

Analytic plan.

Aim 1. Test the direct effects of the 6-module eCPP on parenting outcomes (parenting behavior, self-efficacy, and stress) and child outcomes (child problem and prosocial behavior) compared to an enhanced usual care control condition among low-income parents with young children seen in primary care. **HYPOTHESIS 1A:** Relative to parents in the control condition, parents in the eCPP condition will report greater improvements in parenting and child outcomes at the 3-month assessment. **HYPOTHESIS 1B:** The improvements in parenting outcomes and child outcomes the eCPP condition relative to the control condition will be maintained through the 6- and 12-month assessments.

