To determine the effectiveness of the implementation strategy and inform dissemination of the eCPP, a cascaded probability model will be constructed.^{97,98} This will be developed based on the following proportions: (a) the likelihood of clinician adoption at the site [*proportion 1 (pr 1)*], (b) the likelihood of implementation (study introduction) by clinicians at the site [*pr 2*], (c) the likelihood of parent enrollment in the study [*pr 3*], and (d) the likelihood of maintenance of behavior change by the eCPP participants [*pr 4*]. *Pr 4* is defined as the proportion of participants whose parenting and child behavior outcomes are the same or improved at the 12-month data collection compared to the 6-month data collection. The estimated likelihood of parents being introduced to the program will be the product of *pr1* and *pr2*. Second, the compound likelihood of parent enrollment in the study will be the product of *pr1*, *pr2*, and *pr3*. Finally, we will estimate the compound likelihood of maintaining behavior change by examining the product of *pr1*, *pr2*, *pr3*, and *pr4*. This analysis will provide us with two important pieces of information: (1) the probable benefits of the program in terms of how likely it is for parents to achieve maintenance of behavior change and (2) inform us of the phase of the implementation process (as operationalized by *pr1*, *pr2*, *pr3*, and *pr4*) which is likely to interfere with the dissemination of the eCPP.

We will conduct a content analysis of the post-implementation interviews with the clinicians. We will use a coding-based system of content obtained from the interviews using the notes taken during the interview using Atlas.ti software. Atlas.ti allows for the identification, organization, and systematizing of codes that can then be assessed in the context of the clinician interviews. Themes will be summarized by site and used to inform the development of processes and procedures to support the implementation and dissemination of the eCPP in pediatric primary care practice sites.

Bibliography & References Cited

1. Children's Defense Fund. Child poverty in America 2013: State analysis. <http://www.childrensdefense.org/zzz-child-research-data-publications/data/child-poverty-in-america-1.pdf>. Updated 2014. Accessed January 12, 2015.

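### Does the plan leave the Hypothesis 1B test of maintenance at 6 and 12 months undetermined?

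*Combined protocol and SAP*

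**What the plan says.** The relevant text is in the Combined protocol and SAP, Analytic plan, Aim 1. The order of analysis is as follows.

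- First, "a repeated-measures multivariate analysis of variance (assessment x intervention condition) will be conducted", as an overall check across outcomes.
- Next, "We will then test intervention efficacy using multilevel growth models", with three levels (assessment, parent, practice) and the baseline value of the outcome as a parent-level covariate.
- By "setting the intercept at the 3-month assessment, we will be able to test Hypothesis 1A" as the main effect of condition, the plan ties the first hypothesis to one named parameter.
- For the course of the effect once the active phase is over, the plan uses an interaction: "The condition x time interaction will then serve to test differential change in outcome measures following the 3 months of active intervention".
- For Hypothesis 1B, the same sentence then names a second and separate tool, without giving its coefficients or null value: "planned contrasts will be estimated to test Hypothesis 1B (maintenance of intervention effects at 6 and 12 months".

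Hypothesis 1B itself, in the Specific aims, says that the improvements relative to control "will be maintained through the 6- and 12-month assessments". Two other places use the idea of maintenance. Table 5 (RE-AIM, Maintenance row) says "Maintenance of behavior change over time will be assessed as part of the RCT arm of the study" and points to Hypothesis 1B. The Aim 3 cascade defines its fourth proportion as eCPP participants whose outcomes are "the same or improved at the 12-month data collection compared to the 6-month data collection".

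**The concern.** Hypothesis 1A has a named parameter and Hypothesis 1B does not. The word maintained invites two tests:

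- **Level:** the arm difference at 6 and at 12 months, each against zero.
- **Change:** the arm difference at 6 or 12 months minus the difference at 3 months, with no significant loss taken as maintenance.

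No margin for an acceptable loss is given. The form of time is also unstated. The assessment-by-condition layout of the MANOVA suggests visit as a factor, while a growth model with a placed intercept suggests a slope. The visits are unequally spaced, so linear time in months and linear time by visit number are different models.

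If all this were truly open, two analysts could reach opposite conclusions on one of the two Aim 1 hypotheses, and the choice could be made after the results were known. The risk would be greatest when the effect partly fades.

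**Working it through.** **1. What the contrasts compare.** The last sentence of the Aim 1 paragraph gives two tools two jobs. The interaction covers differential change after the active phase, which is the change test. The contrasts cover intervention effects at the two later visits. In the sentence before, the intervention effect at 3 months is the baseline-adjusted difference between arms. Read the same way, the effect at 6 or 12 months is the arm difference at that visit. If the contrasts were the change since 3 months, they would repeat the interaction; with linear time they would be exact multiples of one slope. So the level test is the natural reading, with the interaction reported beside it.

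The fourth proportion in Aim 3 does not compete with this reading. It concerns individual eCPP participants, compares 12 with 6 months, has no control arm and serves the cascade only.

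**2. What is fixed and what is open about time.** The origin (3 months), the model class and the covariate are fixed. The form and scale of time are open.

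**3. Size of the open part.** The documents give no figure to reproduce for this test: no SD, correlation, expected course or significance level. From the documents: 156 per arm and visits at 3, 6 and 12 months. Assumed: full retention, two-sided 5%, residual variance v = 0.64 to 1.0 (SD units), visit correlation r = 0.3 to 0.7, one outcome.

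The estimated arm differences at 3, 6 and 12 months follow N(d, V), with V = v × (2/156) × [(1 − r)I + rJ]. The standard error at one visit under factor coding runs from √(0.64 × 2/156) = 0.091 to √(2/156) = 0.113.

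Linear time in months since the intercept (0, 3, 9) replaces the three estimates by fitted values from the matrix (1/14) × [10 6 −2; 6 5 3; −2 3 13]. For a true course of 0.40/0.20/0.20:

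- 3 months: (10×0.40 + 6×0.20 − 2×0.20)/14 = 4.8/14 = 0.34
- 6 months: (6×0.40 + 5×0.20 + 3×0.20)/14 = 4.0/14 = 0.29
- 12 months: (−2×0.40 + 3×0.20 + 13×0.20)/14 = 2.4/14 = 0.17

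Linear coding therefore overstates the 6-month effect (0.29 against 0.20) and slightly understates the 12-month effect on this course.

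In return it gains precision. If the true course is linear in months, factor-model standard errors are wider by the factor 1/√(r + (1 − r)h), where h is the diagonal element (10/14, 5/14 or 13/14). Over r = 0.7 to 0.3 this is 5 to 12% at 3 months, 11 to 35% at 6 months and 1 to 3% at 12 months.

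**4. Effect on the Hypothesis 1B verdict.** Take the level test, with 3, 6 and 12 months all required to be significant in favour of eCPP (a combining rule assumed here). From 400,000 draws per combination of v (0.64, 0.8, 1.0) and r (0.3, 0.5, 0.7):

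| True course (3/6/12 months) | Supported, factor | Supported, linear months | Verdicts differ |
|---|---|---|---|
| 0.40/0.40/0.40 | 85–98% | 92–99% | 1–9% |
| 0.40/0.30/0.30 | 58–86% | 71–90% | 5–15% |
| 0.40/0.30/0.20 | 35–59% | 41–59% | 5–10% |
| 0.40/0.20/0.20 | 22–47% | 33–49% | 10–17% |
| 0.40/0/0 | under 1% | under 1% | under 1% |

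**The case for a change.** The strongest opposing case is that the level test is inferred and never written down. The hypothesis says maintained, and nothing forbids an analyst from reading a non-significant change as maintenance. On that rule the two tests would disagree in 23 to 40% of trials for 0.40/0.30/0.30, 32 to 49% for 0.40/0.30/0.20 and 29 to 44% for 0.40/0.20/0.20. The rule also rewards lost data: for 0.40/0.20/0.20 with v = 0.64 and r = 0.5, going from 156 to 109 per arm raises its pass rate from 24% to 35%, while the level test falls from 44% to 29%.

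These figures are correct under their assumptions, but the plan nowhere adopts that rule. They show that it would be a poor one, and that is a further reason why a competent analyst would not choose it.

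On coding, the 6-month comparison taken alone changes verdict between months and factor coding in 34 to 50% of trials for 0.40/0.20/0.20. That stands for this visit and this sharp early drop. It falls to 7 to 22% for 0.40/0.30/0.20, and because the hypothesis covers both later visits, the combined verdict moves much less.

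It also stands that the plan states neither whether both visits must succeed nor the form of time. One clarifying sentence would do no harm. The consequence for RE-AIM is limited: the Maintenance row also draws on recruitment rates, follow-up orientation sessions and clinician interviews, and the cascade has its own explicit definition.

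**Conclusion.** The concern does not call for a change. The plan implies the Hypothesis 1B contrasts without writing them out: the arm differences at 6 and 12 months against zero, with the interaction separately addressing change after 3 months. An analyst who follows that reading reaches a sound result. The form of time is a genuine omission, but factor and linear coding are both acceptable, and each buys something: unbiased visit-specific effects in one case, tighter standard errors in the other.

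The remaining looseness changes the combined verdict in about 5 to 17% of trials on the three partial-fading courses examined, and less where 0.40 SD is fully kept (1 to 9%) or fully lost (under 1%). These sizes rest on assumed variances, correlations, courses, significance level and combining rule, on full retention and on a single outcome. They leave out the preliminary MANOVA and the multiplicity of outcomes. The reading of the text does not depend on them.
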